6.2.3 Other efficacy

Taste and texture of the pediatric formulation(s)

Taste and texture is assessed by use of a questionnaire at the beginning (Day 0) and at the end of the main study (week 24 or end of treatment visit). The assessment is completed only for subjects who received study medication via oral suspension. It will be analyzed descriptively using frequency tables.

Right heart catheterization (RHC)

RHC may be conducted on medical reasons during the study. It will be analyzed descriptively by sample using summary statistics and tabulated with change in RHC parameters (if available) obtained from RHC performed before study enrollment and during study conduct.

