**Q.4. Would you like to drink this medication (suspension) again?**

Show and describe the list (3-point-Scale)

- |                       |                          |   |
|-----------------------|--------------------------|---|
| YES                   |  | 😊 |
| NO                    |  | 😞 |
| I DON'T KNOW / UNSURE |  | 😐 |

Please proceed with questions Q.5. to Q.7., IF:  
➤ Questions Q.3. or Q.4. were answered with "NO"!

**Q.5. Now I would like to ask you a little bit more about the medication. I will read out loud a few statements to you concerning the taste of the medication (suspension). Please tell me for every statement if it applies or not.**

- Show and describe the list (3-point-Scale); only one answer is possible per statement.
- Please change the order of the statements for each child (randomization) e.g. for the first child start with the item sweet; for the second child start with the item bitter and so on.
- If the child doesn't understand the description of the taste, please provide examples (e.g. "like sugar" for sweet, "like lemon" for sour), if possible. If the child still doesn't understand the description of the taste, please tick "not understood."

The medication (suspension) tastes ....	Yes 	No 	I don't know/ Unsure 	Not understood
Sweet				
Sour				
Bitter				
Salty				
Disgusting				
Fruity				

**Other:** if applicable, capture other expressions regarding the taste

.....

.....

.....

**Q.6. Now I would like to know how the medication (suspension) feels in your mouth. Please tell me for every statement if it applies or not.**

- Show and describe the list (3-point-Scale); only one answer possible per statement.

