3.2 Dosing overview

The individual optimal study dose will be defined during the titration phase of 8 weeks. The last dose administered during the titration phase will be administered during a 16-week maintenance phase. Subjects of the older age cohort (≥ 12 to < 18 years) are treated first. After 5 subjects of this age cohort were treated for 24 weeks, an independent DMC will provide recommendations to the further conduct of the study.

Riociguat is administered to all subjects using an individual dose titration scheme according to a body weight-adjusted dose to achieve a similar exposure as that observed in adults treated for PAH. The individual optimal (maintenance) dose is to be determined based on patient's monitoring of systolic blood pressure, well-being and clinical status. For children with < 50 kg body weight at screening, a body weight adjusted dosing will be applied. Children with ≥ 50 kg body weight at screening will receive adult doses.

[figure not shown]
In subjects with a body-weight below 50 kg at screening, riociguat is administered as oral suspension TID with or without food. Subjects with a body-weight ≥ 50 kg at screening receive riociguat as tablet formulation.

The following tablet strengths are available: 0.5 mg, 1.0 mg, 1.5 mg, 2.0 mg, and 2.5 mg. An oral suspension formulation of 0.15 mg/mL is also available.

Subjects with < 50 kg body weight at screening start with body-weight adjusted riociguat dose equivalent to the exposure of 1.0 mg TID in adults. Subjects with ≥ 50 kg body weight at screening start with dose 1.0 mg TID. During the individual titration period, the dose is up-titrated every 2 weeks (± 2 days) at the discretion of the investigator, based on subject's peripheral systolic blood pressure (SBP) and general tolerability measured at trough before intake of the next higher dose of riociguat. The maximum dose is the dose equivalent to the exposure of 2.5 mg in adults TID. Dose reductions for safety reasons are allowed at any time. The individual dose titration period does not exceed 8 weeks.

Dosing steps and dose equivalents in adults are shown in Figure 3–1 :

Figure 3–1: Dosing Schedule

TID = three times a day; V = Visit

At each titration visit, the individual dose is assigned based on the following algorithm where peripheral SBP will be measured (by oscillometry with the same calibrated oscillometry unit in each center) at trough before intake of the first dose of the day.

Dose titration algorithm

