4.1 General Principles

The statistical evaluation will be performed by using the software package Statistical Analysis Software (SAS) release 9.4 or higher (SAS Institute Inc., Cary, NC, USA). All variables will be analyzed by descriptive statistical methods.

1. The number of data available and missing data, mean, standard deviation (SD), minimum, 25% and 75% quartiles, median, and maximum will be calculated for metric data. Mean, median, quartiles and SD will be reported to one decimal place greater than the data were collected. Minimum and maximum values will be reported with the same precision as they were collected. The same metrics will be calculated for the change in parameters between Baseline and visits after Baseline.
2. Frequency tables will be generated for categorical data. These include the counts and percentages of each category including the category 'missing' as a separate category, if applicable. Percentages will be calculated using a denominator of all subjects in the specified population, and the percentage values will be reported to one decimal place. If an incidence is $< 0.1\%$ but $> 0\%$, it will be displayed as " $<0.1\%$ ".
3. If no data exists for a table, an empty table will be provided. The text in that table should read "No data matched the selected criteria".
4. For tables that fit horizontally on a single page, and that are more than one page in length, "Continued" will be added to the bottom of all but the last page. The word "Continued" must be added to the title for all pages after the first page and to the bottom of the page for all pages from the first to the second to last page.
5. For event-based tables the number of subjects should be displayed next to the treatment with the syntax "(N=x)". For tables where the N is the number of subjects and also used as the denominator "N=x (100%)" is to be used.
6. In frequency tables, if "n=0", then only "0" should be displayed; "(0.0%)" will not be displayed.
7. When numerator and denominator values are "0", do not use brackets. Use the following: "0/0", not "0/0 (%)".
8. All listings will be presented for subjects with their subject identifier, age at screening, sex and race.

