5.1 Assignment of analysis sets

Final decisions regarding the assignment of subjects to analysis sets will be made during the VRM and documented in the VRR (see section 4.6).

Safety analysis set (SAF)

A subject will be included in the SAF (equivalent to full analysis set, FAS) if he/she is assigned to receive study medication and has received at least one dose of the study medication.

Listing only set (LOS)

All subjects who signed informed consent for treatment eligibility at screening but could not be assigned to safety analysis set defined above. Their data will be presented in individual subject data listings in CSR section 16.2.1 and will not be included in any statistical analyses.

6. Statistical Methodology

The analysis will include data from screening to week 24. Information collected at safety follow-up visit, for subjects not continuing in the LTE phase, will be included in tables, if applicable. LTE phase data collected until the cut-off date from subjects already in the LTE phase will be listed only.

The cut-off date will be defined after all treated subjects completed the 24 week treatment period assessments or safety follow-up visit is completed for all subjects who are not continuing in the LTE phase, except those who are lost to follow-up. The cut-off date will be defined by the sponsor, allowing time for data cleaning.

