6.2.2 Secondary efficacy

Efficacy is evaluated in exploratory manner based on SAF and assessed as change from baseline to end of treatment (week 24). All data except PedsQL data are part of the DMC package.

It includes following endpoints:

- **6-Minute Walking Distance (6MWD)**

6MWD will be analyzed descriptively by summary tables. Time points of efficacy assessments are at baseline and week 24.

- **WHO functional class**

WHO functional class will be analyzed descriptively using frequency tables. Time points of efficacy assessments are at baseline and week 24.

- **Laboratory biomarker (NT-proBNP or BNP)**

NT-proBNP or BNP will be analyzed descriptively by summary tables. Time points of efficacy assessments are at baseline and week 24.

- **Child Health-related Questionnaire (SF-10)**

SF-10 scores (Physical Summary Score, and Psychosocial Summary Score) will be analyzed descriptively by summary tables. Time points of efficacy assessments are at screening and week 24.

- **Generic Core Scales self-report (PedsQL)**

Summary scores of all three types of questionnaires (Young Child Report (age: 5-7), Child Report (age: 8-12), Teen Report (age: 13-18)) will be analyzed overall (all age groups together) and by age cohort (≥ 6 to < 12 years and ≥ 12 to < 18 years) by summary tables. Time points of efficacy assessments are at screening and week 24.

Following Summary Scores will be analyzed:

- Physical Functioning Dimension
- Emotional Functioning Dimension
- Social Functioning Dimension
- School Functioning Dimension
- Physical Health Summary Score (equal to Physical Functioning Dimension)
- Psychosocial Health Summary Score
- Total Score

• **Echocardiography**

There are following echocardiography parameters assessed:

Table 6–1: Echocardiography parameters

General description (in clinical study protocol)	Parameters in data
Pulmonary arterial systolic pressure (PASP)	Pulmonary artery systolic pressure
Tricuspid annular plane systolic excursion (TAPSE)	Tricuspid annular plane systol. Excursion
Pericardial effusion	Finding for pericardial effusion
	Pericardial effusion
Left ventricular eccentricity index	Left ventricular eccentricity index
Right atrial pressure	Estimate of mean right atrial pressure
Right ventricular pressure by tricuspid regurgitant jet velocity	Tricuspid regurgitation peak velocity
Acceleration time of pulmonary flow	Pulmonary artery acceleration time

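### Taste questionnaire: the SAP's percentage rule puts Q5-Q7 over children who were never asked, and leaves the denominator for Q1-Q4 unclear

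*SAP*

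**What the plan says.** Taste and texture of the paediatric formulation is listed as an 'other' objective in Protocol Section 2 and SAP Section 2, and Protocol 6.3 requires a questionnaire at the start and at week 24.

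- **Who answers.** SAP 6.2.3: "The assessment is completed only for subjects who received study medication via oral suspension". On the analysis it says only: "It will be analyzed descriptively using frequency tables".
- **The general rule.** SAP 4.1 item 2: "Percentages will be calculated using a denominator of all subjects in the specified population". Frequency tables give counts and percentages per category, "including the category 'missing' as a separate category, if applicable". There is no category for an item that did not apply.
- **The analysis sets.** SAP 5.1: "A subject will be included in the SAF (equivalent to full analysis set, FAS) if he/she is assigned to receive study medication" and has taken at least one dose. The only other defined set is the listing-only set, which is kept out of all statistical analyses. SAP 6.2.2 states "Efficacy is evaluated in exploratory manner based on SAF"; SAP 6.2.3 names no population.
- **Formulation.** SAP 3.2: "Subjects with a body-weight ≥ 50 kg at screening receive riociguat as tablet formulation". Such children belong to the safety set.
- **The skip.** After Q4, Protocol Appendix 4 instructs the interviewer: "Please proceed with questions Q.5. to Q.7., IF" Q3 or Q4 was answered NO. The SAP does not mention this.

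**The concern.** Two filters stand between a treated child and an answer on taste. The first is formulation: a child on tablets has no suspension to judge. The second is the skip: a child who did not answer NO to Q3 or Q4 is never asked whether the medicine was sweet, bitter, sandy or sticky, or left a bad taste. A percentage over a group wider than those asked mixes the answer with the chance of being asked. A low figure for 'bitter' could mean that few children found it bitter, or that few were asked.

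Protocol 7.1 and SAP 4.3 also commit to reporting missing-data proportions. With 'missing' as the only available category, children skipped by design look like lost data, and the tables cannot separate the two.

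**Working it through.** The documents give no taste figure, so there is nothing to reproduce. The check sets the rule against the questionnaire and then illustrates the size with assumed counts.

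**Inputs.** From the documents: the denominator rule and 'missing' category (SAP 4.1), the safety set (SAP 5.1), suspension-only completion (SAP 6.2.3) and the skip (Protocol Appendix 4). The round number 20 echoes the minimum of 20 children on an ERA in Protocol 4.1. Assumed, because the documents do not give them: the number on suspension, the number asked and the answers.

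**Formula.** Let *y* children choose a response, *d* be asked the item, and *D* be the denominator used. Then

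reported share = *y*/*D* = (*y*/*d*) × (*d*/*D*).

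The factor *d*/*D* is the dilution. It is also the highest percentage the item can reach.

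**Q5-Q7 (assumed: 20 treated, 12 on suspension, 4 with NO to Q3 or Q4, 3 of these say 'bitter').**

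| Denominator | Calculation | Result | Ceiling *d*/*D* | Not asked, shown as missing |
|---|---|---|---|---|
| Children asked | 3/4 | 75% | 4/4 = 100% | 0 |
| Suspension takers | 3/12 | 25% | 4/12 = 33.3% | 12 − 4 = 8 |
| Safety set | 3/20 | 15% | 4/20 = 20% | 20 − 4 = 16 |

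**Other assumed counts, safety set of 20.**

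| On suspension | Asked | Say yes | Over asked | Over suspension takers | Over safety set |
|---|---|---|---|---|---|
| 10 | 5 | 4 | 80.0% | 40.0% | 20.0% |
| 15 | 7 | 5 | 71.4% | 33.3% | 25.0% |
| 20 | 4 | 3 | 75.0% | 15.0% | 15.0% |

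In the last row every child takes suspension, so formulation plays no part. The Q5-Q7 dilution remains because it comes from the skip.

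**Q1-Q4.** Every suspension taker is asked these, so *d* is the number on suspension. If *D* is suspension takers, *d*/*D* = 1 and there is no dilution. If *D* is the safety set, the ceiling for any answer is 5/20 = 25%, 10/20 = 50%, 15/20 = 75% or 20/20 = 100% for 5, 10, 15 or 20 children on suspension.

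**The case against.** The strongest reply is that SAP 4.1 does not say safety set. It says the specified population, and the only population language in 6.2.3 is the suspension sentence. The SAP often restricts a table with one sentence in its own section: PK statistics to patients with a valid value (6.3), growth tables without Down syndrome and BMI for non-Asian children (6.4.7). SAP 4.1 also allows for other denominators. Item 5 singles out tables where N serves as the denominator too, and item 7 gives a format for 0/0. Table shells and display standards, which are not among the documents, may settle the matter.

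Most of this stands for Q1-Q4. A reader might infer that all taste percentages are diluted by tablet takers; the text does not establish that, because reading suspension takers as the specified population is reasonable. A reader might also infer that a child of 50 kg or more never takes the suspension. Protocol 5.4 says otherwise, since suspension is supplied if weight falls below 50 kg, and Table 5-2 lists suspension volumes for that weight band.

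Nor is it exact to call those asked Q5-Q7 children who disliked the medicine. NO to Q4 alone triggers the items, so a child who liked it can be asked. Q3 also allows an unsure answer, so the number who liked the medicine cannot be found by subtracting those asked.

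The reply does not rescue Q5-Q7. Accepting suspension takers as the population still places skipped children in the denominator, and nothing in the SAP points to the skip. Unseen shells might do so, but 6.2.3 does not refer to them.

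Finally, the tables will show counts, so a careful reader can add up the answers to an item and recompute its percentage. That limits the harm. It does not separate a child who was not asked from one who was asked and has no recorded answer.

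**Conclusion.** The point holds for Q5-Q7 under either reading of the population: the written rule divides by children who were never asked and labels planned skips as missing. For Q1-Q4 it holds only if the safety set is used, and SAP 6.2.3 leaves that open.

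The size cannot be known from the documents, because it depends on how many children take suspension and how many answer NO to Q3 or Q4. With the assumed counts above, 75% among those asked is reported as 25% or 15%.

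The importance is minor. This is an 'other', purely descriptive endpoint with no decision rule, and the primary safety and PK results are untouched. A reader might infer that the percentages would say nothing about the formulation. That goes too far: the numerators are answers about the formulation, and it is the denominators that mislead.

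**What to change.** Add to SAP 6.2.3:

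- Percentages for Q1-Q4 use children taking suspension at that visit.
- Percentages for Q5-Q7 use children who answered NO to Q3 or Q4 at that visit.
- Each result is shown as n/N, with 'not asked' (tablets, or skipped by design) separate from 'missing' (asked or due to be asked, but no answer recorded).

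Tying the rule to the visit covers children whose formulation changes. The cost is a short addition to the SAP and a derived flag from the formulation record and the Q3 and Q4 answers. It needs no new data and no change to the questionnaire or the conduct of the trial.

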6.3 Pharmacokinetics/pharmacodynamics

BAY 63-2521 and M1 (BAY 60-4552) peak and trough concentrations will be summarized per visit, separated according to actual dose for peak concentrations and according to previous dose for trough concentrations.

The analyses will be focused on descriptive statistics for patients with a valid PK value, and the frequency of patients with invalid or missing PK value by time point will be shown. The following statistics will be calculated for each of the sampling points: arithmetic mean, standard deviation and coefficient of variation (CV), geometric mean, geometric standard deviation (re-transformed standard deviation of the logarithms), and CV, minimum, median, maximum value and the number of measurements.

Means at any time will only be calculated if at least 2/3 of the individual data were measured and were above the limit of quantification (LOQ). For the calculation of the mean value a data point below LOQ will be substituted by one half of the limit.

Pharmacokinetic data from this study will be reported under a separate cover.

PK concentrations of the study drug and its metabolites will be listed and tabulated.

For pharmacodynamics see section [6.2.2](#).

6.4 Safety

The primary objective of this study is to evaluate safety and tolerability of riociguat in children with PAH. Primary endpoint of the study is: Change from baseline to end of treatment (week 24) of safety and tolerability.

Beside the number of subjects who discontinued prematurely, safety and tolerability will be assessed by incidence of adverse events and serious adverse events, recording of ECGs, vital signs, body weight, left hand X-ray and laboratory panel.

Safety data will be presented in data listings, and summarized in tables for subjects in the SAF.

AEs will be coded according to the MedDRA, last available version, and analyzed by SOC and PT.

6.4.1 Adverse event

Adverse events are considered to be treatment-emergent adverse events (TEAE) if they have started or worsened after first application of study drug up to 2 days after end of treatment with study drug.

The safety evaluation of AE data will include:

- Overall summary of AEs
- Overall summary of TEAEs
- TEAEs and by SOC and PT (overall, serious, study drug related, study drug related serious, of special interest, not related to study drug, TEAEs resulting in discontinuation of study drug, study drug related resulting in discontinuation)
- TEAEs by SOC and PT and by maximum intensity (overall, serious, study drug related, study drug related serious, TEAEs of special interest, TEAEs resulting in discontinuation of study drug)
- TEAEs by SOC and PT and by worst outcome (overall, serious, study drug related, study drug related serious, TEAEs of special interest, TEAEs resulting in discontinuation of study drug)
- Common ($\geq 5\%$) TEAEs by PT, common ($\geq 5\%$) serious TEAEs by PT, common ($\geq 5\%$) study drug related TEAEs by PT
- Listings of serious TEAEs, serious TEAEs with outcome of death, serious TEAEs leading to discontinuation of study drug, TEAEs of special interest, TEAEs of special interest leading to discontinuation of study drug, TEAEs leading to discontinuation of study drug and deaths.

Adverse events of special interest are: Hemoptysis, Hypotension and Skeletal related events.

For each SOC and PT, summaries will be made with respect to the proportion of subjects having at least one occurrence of that event in dosing group (0.5 mg, 1.0 mg, 1.5 mg, 2.0 mg, 2.5 mg TID) and overall during the study.

All adverse event tables will be presented overall (all ages). In addition, presentation will be done by age group and concomitant PAH medications for overall summary tables and Common ($\geq 5\%$) TEAEs by PT, common ($\geq 5\%$) serious TEAEs by PT, common ($\geq 5\%$) study drug related TEAEs by PT tables.

Non-TEAEs will be listed only.

Following outputs are part of the DMC package:

- Overall summary of TEAEs
- TEAEs by SOC and PT
- Serious TEAEs by SOC and PT
- Study drug-related TEAEs by SOC and PT
- Serious study drug-related TEAEs by SOC and PT
- TEAEs of special safety interest by SOC and PT
- Listings of deaths
- Listings of all AEs with information of serious adverse events (SAEs), AEs leading to discontinuation of study drug and AEs of special interest.

In addition all adverse events terms and investigator terms are tabulated.

6.4.2 Laboratory data

Following laboratory parameters are collected: complete blood count (CBC) of hematology parameters and general chemistry parameters Creatinine, SGOT/AST, SGPT/ALT, blood urea nitrogen (BUN), gamma-glutamyltransferase (GGT), uric acid, total bilirubin, albumin, sodium, potassium, calcium, phosphate and glomerular filtration rate (calculated based on Schwartz formula for non Japan population and Japan-specific formula for Japan population). All data will be evaluated via local laboratory. Descriptive analysis of laboratory parameters (AST, ALT, BUN, creatinine, GGT, uric acid, total bilirubin, albumin, sodium, potassium, calcium, phosphate, CBC and Glomerular filtration rate) and their corresponding changes from baseline will be presented. Values that are outside the labor specific reference ranges will be considered as laboratory abnormality.

Data will be summarized by visit using frequency tables for values within/outside reference ranges. Laboratory data outside the standard reference ranges and clinically relevant abnormal laboratory values will be flagged in listings.

Laboratory data will be presented overall (all ages).

Additionally a table of Treatment emergent specific laboratory abnormalities will be produced including SGOT/AST > 3*ULN, SGPT/ALT > 3*ULN, Bilirubin > 2*ULN, Glomerular filtration rate <30 mL/min/1.73m².

Laboratory data are part of the DMC package.

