#### 7.4.1 Safety analysis - amended

The primary objective is to evaluate the safety and tolerability of riociguat in children with PAH. Primary endpoint of the study is: Change from baseline to end of treatment (week 24) of safety and tolerability assessed by incidence of adverse events and serious adverse events, recording of vital signs and left-hand X-ray and laboratory panel.

The safety evaluation of adverse event (AE) data will include:

- The incidence of treatment-emergent AEs (TEAEs). Adverse events are considered to be treatment-emergent if they have started or worsened after first application of study drug up to 2 days after end of treatment with study drug.
- Tables of serious and/or drug-related treatment-emergent AEs, treatment-emergent AEs leading to discontinuation of study drug and AEs of special safety interest.

- The incidence of AEs during pre-treatment and during follow-up (i.e. AEs occurring more than 2 days after end of treatment with study drug).
- Listings of serious adverse events (SAEs), AEs leading to discontinuation of study drug and AEs of special safety interest.
- Descriptive summaries of mortality in the study.
- Listing of deaths in the study period, including day of death relative to start and stop of study drug and cause of death.

The safety evaluation of laboratory data will include:

- Incidence rates of treatment-emergent laboratory values outside of normal range
- Incidence rates of pre-specified laboratory data abnormalities
- Descriptive analysis of laboratory parameters (AST, ALT, BUN, creatinine, GGT, UA, T-Bil, Alb, Na, K, Ca, P, and CBC) and their corresponding changes from baseline

Other evaluations of safety data will include:

- Descriptive analysis of body weight, vital signs, ECG parameters, left hand x-ray and their corresponding changes from baseline.
- Tabulation of ECG status pre-dose, 2 and 4 hours post treatment-initiation.
- Incidence rates of treatment-emergent ECG abnormalities.

Time points of assessment: Assessment of adverse events at baseline, at all visits in the titration phase and maintenance phase, and every 3-4 months in the extension phase. Left hand x-ray at baseline, end of study treatment period (week 24) and every 12 months until growth plates are closed.

For details on safety variables, see section 6.2.

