6.4.5 Electrocardiogram (ECG)

ECG will be summarized by visit. In addition, at Day 0, pre-dose, 2 and 4 hours assessment will be evaluated. Investigator assessment and other parameters, including changes from baseline, will be tabulated.

Data will be presented overall (all ages), by age group and concomitant PAH medications. Refer to table shells for more information about the subgroup presentation.

ECG outputs are part of the DMC package.

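### The SAP text leaves out two incidence analyses planned in the protocol: treatment-emergent out-of-range laboratory values and treatment-emergent ECG abnormalities

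*SAP*

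**What the plan says.** Protocol 7.4.1 lists three separate incidence analyses that matter here:

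- "Incidence rates of treatment-emergent laboratory values outside of normal range"
- "Incidence rates of pre-specified laboratory data abnormalities"
- "Incidence rates of treatment-emergent ECG abnormalities"

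SAP 6.4.2 treats a value outside the laboratory's reference range as an abnormality. It then plans four displays:

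- Counts in and out of range: "Data will be summarized by visit using frequency tables for values within/outside reference ranges".
- Descriptive statistics for each parameter "and their corresponding changes from baseline will be presented".
- Listings that flag out-of-range and clinically relevant values.
- A threshold table: "Additionally a table of Treatment emergent specific laboratory abnormalities will be produced including SGOT/AST > 3*ULN". The other entries named are ALT above 3*ULN, bilirubin above 2*ULN and GFR below 30 mL/min/1.73m².

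SAP 6.4.5 says "ECG will be summarized by visit" and adds the Day 0 assessments before dosing and at 2 and 4 hours. It also says "Investigator assessment and other parameters, including changes from baseline, will be tabulated".

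SAP 4.5 sets a window of 2 calendar days after the last dose within which values count as treatment-emergent, and it sends unscheduled measurements to the listings. SAP section 7, which covers the document history and changes in the planned analysis, mentions no change to the laboratory or ECG analyses.

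**The concern.** A by-visit count answers how many children are abnormal at this visit. An incidence of treatment-emergent abnormality answers how many children became abnormal on riociguat. The protocol asks the second question and the SAP text answers the first.

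The difference matters more than usual here. The trial has a single arm, and every child enters on an ERA, a PCA or both, so the child's own baseline is the only comparator. A percentage abnormal at week 24 mixes abnormalities that predate riociguat with those that appeared during treatment. New cases and recoveries can cancel within the same row of the table.

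Unscheduled tests add to this. Protocol 6.2 collects extra laboratory values when they are medically required. Under SAP 4.5 these go to listings, so a value prompted by clinical concern may not reach the by-visit table. SAP 4.3 does admit unscheduled values when it derives a last-visit value, but that captures only the final observation.

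**Working it through.** **Step 1. Compare the two documents item by item.**

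| Protocol 7.4.1 item | Counterpart in the SAP text |
|---|---|
| Treatment-emergent out-of-range laboratory values | None. SAP 6.4.2 has by-visit counts only |
| Pre-specified laboratory abnormalities | Present: the threshold table in SAP 6.4.2 |
| Treatment-emergent ECG abnormalities | None. SAP 6.4.5 has by-visit summaries and changes from baseline |

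The first gap covers CBC, electrolytes, albumin, GGT, uric acid and BUN, and also AST, ALT and bilirubin values that are out of range but below the named cut-offs.

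The mismatch does not look like a timing effect. The notes to Protocol 7.4.1 cite Amendments 3, 5 and 6, and the SAP states that it is based on protocol amendments up to Amendment 12. The change table for Amendment 14 does not list section 7.4.1.

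**Step 2. Ask whether by-visit counts can give the incidence.**

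The documents state no figure to reproduce. Protocol 7.5 says that the sample size rests on feasibility, and no abnormality rates are given. The check therefore uses bounds.

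Inputs:
- N = 20, the protocol's minimum number of children on an ERA. All are assumed to be measured at each time point.
- b = number abnormal at baseline and w = number abnormal at a later visit. Both are assumed values, shown over a range.

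Formulas:
- Children at risk of a new abnormality: N − b.
- New cases at the later visit: at least max(0, w − b) and at most min(w, N − b).

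For b = w = 4, the number at risk is 20 − 4 = 16. The minimum is max(0, 0) = 0 and the maximum is min(4, 16) = 4. Incidence therefore lies between 0/16 and 4/16, that is 0% to 25.0%.

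| b = w | At risk | New cases possible | Incidence possible |
|---|---|---|---|
| 2 | 18 | 0 to 2 | 0% to 11.1% |
| 4 | 16 | 0 to 4 | 0% to 25.0% |
| 5 | 15 | 0 to 5 | 0% to 33.3% |
| 8 | 12 | 0 to 8 | 0% to 66.7% |

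**Step 3. Use both on-treatment laboratory visits.**

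Protocol 6.2 schedules laboratory tests at V0 (or uses historical values), V5 and V9. With 4 of 20 abnormal at each of the three time points, the number of children newly abnormal at V5 or V9 is at most min(16, 4 + 4) = 8 and at least 0. Incidence lies between 0/16 and 8/16, that is 0% to 50%.

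In every row the by-visit table shows the same percentage at each time point. A treatment-emergent table would give one value instead of a range.

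**The case against.** The strongest reply is that this is a gap in one type of summary table and that much else remains.

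- A reader might infer that the SAP has abandoned treatment-emergent laboratory analysis. It has not. The threshold table covers the protocol's pre-specified item, its wording leaves room for further entries, and SAP 4.5 still defines a treatment-emergent window for values. Nothing in the SAP says that the two protocol analyses were dropped on purpose.
- A reader might infer that new abnormalities will be hidden. That goes too far. Changes from baseline are summarised for every parameter, out-of-range values are flagged child by child, and Protocol 8.5 has clinically relevant laboratory abnormalities reported as adverse events. The baseline column also sits beside the later visits. What stands is narrower: changes from baseline do not count children who cross a reference limit, adverse events capture only values judged relevant, and listings leave the counting to the reader.
- A reader might infer that the primary laboratory measure is lost. Protocol 6.2 defines that measure as change from baseline to week 24, which SAP 6.4.2 keeps. ECG is listed there among other safety outcomes, also as change from baseline, and is kept too.
- A reader might infer that haemoglobin must join the threshold table, because Amendment 3 added CBC sampling in view of anemia reported with bosentan. The same rationale says that adult studies gave no indication of laboratory changes due to riociguat, and the protocol does not say which abnormalities are pre-specified. Adding haemoglobin there is optional.
- SAP 4.1 points to sponsor display standards, and SAP 6.4.5 to table shells for subgroup presentation. These are not in the documents and could contain the missing tables. That limits the claim to the SAP text, but a protocol-stated analysis should still be named in the SAP or its removal declared.

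**Conclusion.** The point holds in limited form. The plan is wrong as written because the SAP text does not deliver two descriptive analyses that Protocol 7.4.1 states, and SAP section 7 does not declare their absence. By-visit counts cannot stand in for them: with assumed counts of 4 of 20 abnormal before treatment and at week 24, the incidence among the 16 children at risk could be anything from 0% to 25%.

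These counts show what is possible, not what is likely, because the documents give no abnormality rates. The bounds assume N = 20 with complete data. No decision rule depends on these tables and the study is descriptive throughout, so the consequence is a less informative safety summary and an undeclared departure from the protocol, not a failure of the primary measure. The correction should be made, since it is specific and cheap.

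**What to change.** In SAP 6.4.2 and 6.4.5, add the protocol's treatment-emergent incidence tables:

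- **Scope:** each laboratory parameter, low and high separately, with haemoglobin included as part of CBC; and ECG abnormality, stating which assessment defines abnormal.
- **Numerator:** children newly abnormal from after the first dose to the last dose + 2 days, with unscheduled values included.
- **Denominator:** children not abnormal in that direction at baseline who have at least one post-baseline value.
- **Children already abnormal at baseline:** show them in a baseline-to-visit shift table, so that they stay visible although they fall outside the denominator. The SAP already plans a shift table for Tanner stage.

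If the tables already exist in shells or sponsor standards, name them in these two SAP sections. If the sponsor chooses not to produce them, record the removal as a change from the protocol in SAP section 7.

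The cost is SAP wording and standard programming. No new data are needed.
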